behavioural signs of RAD that could indicate a potential RAD diagnosis. In-depth assessments of RAD will determine whether sufficient RAD symptoms are present for the child to enter the pilot trial. For the screening phase, active consent will be provided by the foster carer only, as it does not involve direct contact with the foster child. A letter will be sent to all parents explaining the study and offering them the opportunity to ask questions and opt-out if they have concerns. Parents will be given a minimum of two weeks to notify the Local Authority or the research team if they wish to opt out from the screening. If a child meets the RAD threshold full consent from those holding parental responsibility would then be obtained and the child and foster carer (if all parties are happy to proceed) will enter the pilot trial. Prior to randomisation, the child and foster carer will be invited to attend a baseline assessment and then randomised individually to VIPP-FC or CAU in a 1:1 ratio, stratified by age, gender and site. As this is a pilot trial 40 cases would be randomised in total, which is sufficient to test the feasibility questions described below and estimate approximate confidence intervals for key study parameters. VIPP-FC will be delivered in-home by trained CAMHS practitioners or other appropriately qualified VIPP-trained interveners. Baseline and end of treatment measures will include validated diagnostic assessments of RAD and co-occurring conditions, security of attachment (including disorganized attachment), sensitivity of parenting, child adjustment, carer wellbeing, and the CA-SUS measure of service use. In addition to these outcome measurements, we would also conduct qualitative interviews regarding carers' experiences of the programme and perceptions of VIPP among social workers and VIPP interveners. As a pragmatic study, we would aim to include as representative a group of children as possible and therefore we would aim to apply minimal exclusions based on comorbidity or type of foster care. The pilot RCT will allow us to:

- A. Test the feasibility of identifying sufficient numbers of appropriate cases through social care using appropriate screening instruments and diagnostic assessments of cases screening positively for RAD across several local authorities and locales (rural and urban).
- B. Test the feasibility of recruiting and consenting foster families with children with RAD to an RCT (numbers contacted, consented).

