#### 6.3 RANDOMISATION (PHASE 3)

Participants will be individually randomised in a 1:1 ratio to one of the two treatment arms, CAU + VIPP-FC or CAU-only. Randomisation with minimization will be employed, with minimization factors age (<=4 versus >4), gender and site. Minimization will include a random factor, as implemented in the minimisation program Simin (Wade, Pan, Eaton, Pierro & Ong, 2006). Randomisation will be requested by a member of the research team following completion of all necessary screening and consent procedures, and will be performed by an unblinded member of the trial coordination team. The allocation list will be held in the Trial Master File. We will write to the child's social worker, and VIPP intervener – the latter for those allocated to VIPP-FC. The foster carer, and the individual(s) giving consent on behalf of the child (the parent and/or local authority social worker with parental responsibility as appropriate, see consent section) will be notified of the outcome by letter by the unblinded member of the trial coordination team. The foster carer will also be contacted by telephone (target within 24 hours) to ensure a timely initiation of intervention.

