# 7.3 DATA MANAGEMENT

The data in this study will be collected and processed in accordance with the Data Protection Act (1998). Management of the data will be overseen by the Chief Investigator [name] with support from the Trial Coordinating Team. The case-series and pilot data will be collected by an experienced research assistant who has been trained to work with high-risk populations. The RA will be blind to treatment allocation, with all data issues related to unblinding being handled by the Trial Coordinating Team. Regular supervision with the Chief Investigator, Trial Coordinating Team and core study team (RAs) will ensure the reliability of data collection. Where necessary the RAs will be fully trained and certified in administering all research measures. For data that requires coding using standardized measures we will employ trained reliable coders, ensuring sufficient Inter-Rater Reliability (IRR) amongst coders.

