#### Database

Data for phase 3 (pilot trial) will then be transcribed onto the trial specific database by the RA. The database will be built using REDCap, a secure web application for building and managing online surveys and databases. Data entered onto the database will be anonymised, with participants identified by a randomisation code and no information that could be used for identification included (e.g. date of birth). A master log of participants that are randomised will be kept as a paper document in the Trial Master File, detailing names and randomisation code. The Trial Master File will also be stored in a locked cabinet at UCL, separate from the participant files and accessible only to members of the trial coordination team and Chief Investigator.

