# 11 PROJECT MANAGEMENT

The project will be led by [name] as Chief Investigator, who will retain overall responsibility for the management of the study, including governance, financial oversight and progress reporting. [name] will take responsibility for day-to-day supervision of the research assistant and trial management team, with input from [name]. Each collaborating trust will have a Core study team member allocated to it, who will manage relationships, recruitment set-up, monitoring and communications with their trust and its associated local authorities, with input from the CI where appropriate. [name] will cover CNWL, [name] SLAM, [name] NELFT, [name] LYPFT and TEWV, and the Tavistock and Portman will be jointly overseen by [name] and [name]. This Core Study Team will meet regularly to ensure coordination and monitoring of the practical implementation of systems for recruitment, and the establishment and monitoring of the clinical service delivery of VIPP in each locality. The trial management team will take responsibility for liaison with the sponsor and ethics committees, setting up secure data capture systems for multi-site data collection, and preparing data quality and progress reports for the Steering Committee and HTA. [name] will chair the expert and carer group advising on clinical manual development, and advise on trial design and implementation. [name] will work closely with the CI in preparing the pilot trial from the point of view of implementation within a foster care setting, as well as

contribute to the work of the treatment manual development group. [name] will provide expert input to the treatment development group, and will oversee the measurement aspects of the RAD screening system. [name] will manage the qualitative/mixed methods evaluation. [name] will lead the carer and care-leaver advisory groups, contribute to the expert and carer advisory group and provide regular input to the core study team regarding foster carers' perspectives on study measures, information sheets and clinical process. There will be quarterly full team meetings at which all investigators would be present.

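### The minimisation list is open to the whole trial coordination team and the Chief Investigator rather than only the unblinded person who runs it, an avoidable weakness in concealment and blinding

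*Protocol*

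**What the plan says.** Section 6.3 fixes the method: "Participants will be individually randomised in a 1:1 ratio to one of the two treatment arms, CAU + VIPP-FC or CAU-only". It continues: "Randomisation with minimization will be employed, with minimization factors age (<=4 versus >4), gender and site". A random element is promised but its probability is not given: "Minimization will include a random factor, as implemented in the minimisation program Simin". A member of the research team asks for the allocation once screening and consent are complete. The allocation itself "will be performed by an unblinded member of the trial coordination team. The allocation list will be held in the Trial Master File".

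Section 7.4 (Database) puts a master log of randomised participants, with names and randomisation codes, in the same Trial Master File. The file is kept in a locked cabinet, "separate from the participant files and accessible only to members of the trial coordination team and Chief Investigator".

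Section 7.3 says that the research assistant collecting the data is blind to allocation and that the Trial Coordinating Team handles matters of unblinding. It then states: "Regular supervision with the Chief Investigator, Trial Coordinating Team and core study team (RAs) will ensure the reliability of data collection".

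Under section 6.3, carers, social workers, those who consented for the child and, for children allocated to VIPP-FC, interveners are told the arm.

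**The concern.** Section 6.3 gives the act of allocation to one unblinded person. The access rule in section 7.4 is wider than that: it admits the rest of the coordination team and the Chief Investigator, who need the list neither to run the allocation nor to supervise data collection.

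Under minimisation, access to past allocations matters more than under simple randomisation. The favoured arm follows from the running totals and the next child's age group, gender and site, all known before the allocation is requested. A person with the list can therefore form a better-than-even view of the next arm.

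Two protections are weakened. One is concealment before entry, which counts here because carers and interveners know the arm afterwards. The other is the blinding of the research assistants, because those who supervise them can look up every child's arm. The quantity mainly exposed is test h.2 in section 10, the post-treatment difference between groups.

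**Working it through.** **Step 1: who can see the list.**
- Section 6.3: one unblinded team member runs the program, and the list goes into the Trial Master File.
- Section 7.4: the file is open to all members of that team and to the Chief Investigator.
- Section 7.3: the Chief Investigator and the Trial Coordinating Team supervise the research assistants.

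I read the two team names as one group. I also read the list as the running record of allocations made, since minimisation cannot produce one in advance.

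**Step 2: inputs for predictability.** The protocol states no predictability figure, so there is none to reproduce.
- From the protocol: 40 children (section 4.2: "As this is a pilot trial 40 cases would be randomised in total"), 1:1 ratio, three factors, and 5 NHS Trusts taken as sites (section 5.5).
- Assumed: random-factor probability p (range shown), equally frequent factor levels, equal factor weights, ties split evenly. The guesser also knows the factors of earlier children; the protocol does not say whether the list records them.

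**Step 3: formula.** If a share f of allocations has a favoured arm, a list-holder who always guesses that arm is right with probability

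p × f + 0.5 × (1 − f).

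The share f comes from simulating the 40-child sequence (4,000 trials per setting). With imbalance scored as the sum of absolute marginal differences and 5 sites:
- p = 0.7, f = 0.792: 0.7 × 0.792 + 0.5 × 0.208 = 0.658
- p = 0.8, f = 0.771: 0.8 × 0.771 + 0.5 × 0.229 = 0.731
- p = 0.9, f = 0.758: 0.9 × 0.758 + 0.5 × 0.242 = 0.803

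**Step 4: allow for timing.** Most judgement about entry comes before the allocation request. Section 4.2 puts baseline before randomisation, and section 6.2 aims for baseline within 4 weeks of eligibility. With 40 children over 12 months of recruitment (section 13), 40 × 4/52 ≈ 3 other children are allocated in that time. So I also scored a guess made from the list as it stood three allocations earlier.

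| Assumed p | Correct at allocation | Correct, three allocations earlier |
|---|---|---|
| 0.6 | 58% | 55% |
| 0.7 | 66% | 58% |
| 0.8 | 73% | 60% |
| 0.9 | 80% | 60% |
| 1.0 (no random element) | 87% | 60% |

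**Step 5: sensitivity.** Scoring imbalance by summed counts, which leaves fewer ties, gives 67%, 75% and 82% at allocation for p = 0.7, 0.8 and 0.9, and 59% to 61% three allocations earlier. Using 2 or 8 sites moves the at-allocation figures by about one point and the earlier-guess figures by about two.

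**Step 6: after the change.** With no sight of past allocations, guessing falls to 50%. Someone who knows only the past allocations at their own site (5 sites, summed-count scoring) would still guess 57%, 61% and 64% at p = 0.7, 0.8 and 0.9. Restricting the file does not remove that part.

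**The case against.** The case on the other side is substantial, and much of it stands.

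- **No stated route to entry decisions.** A reader might infer that those who recruit, or who advise on eligibility and consent, hold the list. The protocol does not say so. In section 11, the person "who will manage relationships, recruitment set-up, monitoring and communications with their trust and its associated local authorities, with input from the CI where appropriate" is the core study team member for each trust, and section 7.4 gives the core study team no access to the file. The only link there is occasional input from the Chief Investigator. The supervision in section 7.3 is for reliable data collection, not for eligibility. The judgement of carers' English in section 4.4 is made by a research assistant, who is blind.
- **Size.** A reader might apply the figure of about 75% to every discretionary step. It fits only the timing of the final request. For earlier steps the advantage over chance is about 8 to 10 points on the main scoring.
- **Other supposed faults.** The possible widening of eligibility in section 4.4 is a trial-wide rule, so it cannot follow one predicted allocation. Section 6.3 does not repeat that baseline comes first, but section 4.2 says it, so there is no contradiction. The unstated random-factor probability is detail that may sit elsewhere.
- **Feasibility results.** A reader might expect tests b.1 and c.1 to be distorted. They are proportions pooled over arms, and nothing in the protocol shows a material effect on them.
- **Existing safeguards.** There is a random element, a request made only after consent, a separate person running the program, a blind research assistant, blind scoring of carer sensitivity (section 7.2) and a locked file.

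None of this explains why the whole team and the Chief Investigator need the running list while children are still being allocated and assessed. Blinding the assistant does not conceal the list from the supervisors.

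**Conclusion.** The point holds as an avoidable weakness in concealment and blinding. It is not demonstrated bias. The access rule in section 7.4 is wider than the single unblinded role in section 6.3, and it reaches the people who supervise blinded data collection. A list-holder would guess about 66% to 80% of allocations correctly at the moment of allocation for p of 0.7 to 0.9, and about 58% to 60% three allocations ahead, against 50% under full concealment.

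These figures rest on the assumed p, the assumed factor frequencies and weights, the guesser knowing earlier children's factors, and the reading of the team names as one group. The protocol does not define the team's membership, so the overlap with supervision rests on section 7.3 alone. The consequence is confined mainly to test h.2, an exploratory estimate in a 40-child pilot. The change is still worth making because it is cheap and the pilot's procedures are meant to prepare a full-scale trial.

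**What to change.** In sections 6.3 and 7.4:

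- Restrict the running allocation list, the Simin file and any arm information held with the master log to the unblinded person who runs the allocation.
- State that this person does not supervise the research assistants and does not advise on eligibility or consent.
- Keep any copy in the Trial Master File sealed from the Chief Investigator and the rest of the team until the last outcome assessment, except where an allocation is needed for safety.

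The cost is protocol wording and a change in file access, with no extra participants. The small downside is that the Chief Investigator must ask the unblinded person when an allocation is needed. The abbreviations list names a Clinical Trials Unit, but the protocol gives it no part in randomisation, so this fix does not depend on it.

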# 7 DATA COLLECTION AND DATA MANAGEMENT

The data collection instruments are described in relation to each of the data collection phases (Phases 2 and 3).

# 7.1 PHASE 2B SCOPING STUDY

In the scoping study, single qualitative interviews will be undertaken with key stakeholders in their place of work (social work managers, directors of children's services, CAMHS practitioners or other VIPP interveners, and managers) or at home (foster carers, parents) using semi-structured interview schedules developed iteratively via consultation with the study team and advisory groups.

# 7.2 MEASURES FOR TEST CASE SERIES (PHASE 2A) AND PILOT RCT (PHASE 3)

#### **Screening Measures**

The process of screening of symptoms of RAD is not straightforward, and no fully validated instruments for this purpose exist. This in itself is a significant gap in health technology in this field, as early detection may be critical for improving outcomes for children in care. We propose to use two different instruments that each have their individual limitations, but should make it possible to robustly screen for symptoms of RAD when used together. *The Attachment Screening Assessment* is a new instrument designed specifically to
capture behaviours reflective of the DSM-5 symptoms of RAD and DSED, as well as attachment classifications. The RAD items in particular therefore have greater face validity than the other widely used instrument, the Relationship Problems Questionnaire (RPQ), and have also been found to discriminate well between children in care and those from the community, as well as children with greater overall psychopathology on the SDQ. However, the ASA has thus far not been validated against formal diagnostic assessments, which limits the extent to which it could be used alone as a screening measure. *The Development and Well-Being Assessment (DAWBA)* includes a recently revised set of diagnostic items for DSM-5 RAD. We propose to use these two instruments so that we can test the optimal configuration of items for case identification. This will be achieved through expert consensus and will be combined with adaptive prediction methods as data comes in (specifically, adjusting item weights based on accumulating data from full diagnostic assessments). Since this is a feasibility trial we believe this to be the best way of approaching the uncertainty about the optimal screening tools in this area.

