#### Child:

- (a) living with foster carer(s) in a placement planned to be at least 4 months;
- (b) lived with foster carer for at least 4 weeks
- (c) presence of DSM-5 defined RAD\*
- (d) aged between 11 months and 6 years

Note: as outlined below, because of the uncertain prevalence of RAD in UK foster care populations, the RAD eligibility criterion will be reviewed after 15 cases have been assessed. If fewer than 3 (out of 15) cases scoring over the screening threshold (> 66th percentile on screening measure) actually meet diagnostic criteria, we propose to include sub-diagnostic cases with elevated symptoms in the feasibility trial based on the screening threshold (defined below).

For the pilot case series, we will include a mix of cases that meet the RAD diagnosis and those falling short of the diagnostic threshold in order to explore the suitability of the intervention for both groups of children and expedite the rapid progress of manual refinement.

\*If during the RCT phase number of participants deemed eligible is inadequate to allow delivery of the final study aim (i.e. run the modified VIPP programme for foster care) we will expand the eligibility criteria to include carers with children who do not necessarily meet the RAD criterion.

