#### Pilot RCT

For Phase 3 (the pilot RCT) we will again undertake a screening process to identify children in foster care with RAD. We will then randomise 40 children (and their carers) to receive either VIPP (plus care as usual) or care as usual only. Based on data obtained from the Department of Education from 2014 (which we have corroborated against a selection of figures obtained in 2016 from our participating local authorities) we expect the full population of children in foster care in our target age groups across sites to be in the region of 700. Previous research experience with this population and on the basis of our small pilot screening, we would expect more than 80% of foster carers to take part in the initial screening and return the questionnaires. This estimate seems reasonable, since in the study of Green et al. (2014) of 523 foster families who were approached, only 56 refused (a further 57 were ineligible). Conservatively therefore we will aim for a sample size for the screening stage of 500. In order to identify cases likely to be diagnosed as RAD we will choose cases above the highest 66th percentile for symptoms of RAD (initially based on normative data), leading to a sample size of 150 who would be invited to take part in a more in-depth assessment. We expect a minimum of two thirds of those to agree to take part and complete the assessment. In the randomised controlled trial of the Fostering Changes programme, (Briskman et al., 2012) 77/125 took part in the intervention (following a higher rate of initial interest and questionnaire return), so two-thirds agreeing to an initial assessment is a conservative estimate. From this pool of 100 children we would therefore have scope to identify at least 40 cases that would be eligible for treatment as long as the prevalence of RAD in the high-scoring screened group was 50% (allowing for a further 10% dropout at this stage). Note that we would seek to obtain consent to treatment at the in-depth intake assessment stage, which is why we estimate the throughput of cases to be lowest at this point. As noted already, we lack reliable information concerning the prevalence of RAD in UK foster care and so the 50% prevalence within the population of children exceeding the symptom threshold is subject to uncertainty. Consequently, we propose an interim analysis after 15 cases have been assessed to establish whether the proportion of RAD cases is below this expected proportion. The lower bound of the 95% confidence interval around a proportion of .50 is .22 with a sample size of 15. Thus, identification of fewer than 3 cases out of 15 would suggest that the prevalence is lower than .50. In this event, we propose to widen the eligibility criteria to include children scoring over the screening threshold, but not meeting full RAD diagnostic criteria.

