#### Screening and identification stage

As noted above, the screening process we envisage will be essential to the success of this project and will depend on an effective collaboration with local authorities, who will send out information sheets, initial consent forms and screening measures to all foster carers in the study localities. In addition, local

authorities will send out a letter to all parents explaining the study and the opting-out process, including contact details of the research team. In Phase 2A we will work with up to two local authorities, and will screen approximately 100 children. In phase 3 we will aim for a minimum screening sample of 500 foster carers from 6-10 local authorities. In both cases, all foster carers or special guardians registered with the local authority caring for children under 7 will be sent an information sheet, screening measures, a consent form and contact details of the research team so that they may ask questions if they wish. Screening measures and completed consent forms will be returned using a pre-paid envelope by foster carers to the University or completed online via study database, Redcap. Letters will also be sent to foster care agencies with information and contact details of the research team that may be given to potential participants registered with these organisations. Where self-referrals are received, foster carers will be asked for the child's social worker's details in order for the local authority to initiate the screening process, including contacting the birth parents. As with the families that are contacted through the local authorities, self-referrals will have the contact details of the research team if they wish to discuss the study in more detail. A minimum two-week period will be given between sending out the letter to parents and initiating the child's participation in the study.

Once initial consent forms (paper and online) and screening measures have been received by the research team, they will contact participants, thanking them for their response and re-iterating the research process. Invitations and follow-up phone calls will be made to all foster carers reporting RAD symptoms over the screening cut-off to take part in a face-to-face interview assessment to confirm eligibility (establishing diagnostic status). This interview would take place at the foster carer's home.

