#### **Co-occurring disorder/difficulties**

• *The Development and Well-Being Assessment (DAWBA)* will be used to assess the presence of psychiatric diagnoses co-occurring with RAD, via foster carer interview. The DAWBA is a well-validated diagnostic interview schedule that has been recently extended to children as young as 2 years of age, and has been updated for DSM-5. The DAWBA has been used extensively in clinical trials and epidemiological studies. The system has high-levels of inter-rater reliability and provides automated algorithms for scoring and assigning diagnoses. Note: due to some limitations in its validity for assessing RAD, we rely on the DAI for this diagnosis.

• *Child Behaviour Checklist* (foster carer report): This a very widely used carer-reported questionnaire for assessing children's emotional and behavioural problems and yields well-validated continuous measures of

internalizing problems, externalizing problems, total problems and specific 'syndrome' scales for narrow band symptom areas (such as attention problems, aggression, social problems). It is valid for children from the age of 1.5 years and has age appropriate forms for children aged 1.5-5 years, and 5 years and above.

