# **10** ANALYSIS

Feasibility parameters based on proportions (proportions of cases identified, consented, randomised, completing treatment and outcome measures). Approximate variance estimates will be obtained for the main outcome measures using the upper 80th percentile of the relevant confidence interval (see Brown, 1995). Specifically, we will test the following feasibility parameters:

A. Test the feasibility of identifying sufficient numbers of appropriate cases using screening instruments.

1. Target N for screening tests returned N = 500. Test a.1 = proportion and 95% CI of those returning screening instruments from total sent out.

2. Target N of diagnostic assessments N = 100. Test a.2 = proportion and 95% CI of positively screened cases (above upper 66th percentile) agreeing to full assessment.

3. Target N for positive diagnosis from upper 66th percentile of screened cases N = 50. Test a.3 = proportion and 95% CI of cases where diagnosis is confirmed.

4. Test a.4: initial test of false negative rate = proportion (of 25 cases) and 95% CI of detected diagnoses in random sample of cases not meeting screening threshold.

5. Initial non-parametric ROC curve analysis (total N = 125), based on assumption that DAI diagnosis is gold standard.

B. Test the feasibility of recruiting/consenting foster families with children with RAD to an RCT.

1. Target N of consented cases N = 40. Test b.1 = proportion and 95% CI of cases consenting to enter pilot trial from those meeting entry criteria.

C. Investigate feasibility of randomising to VIPP-FC or CAU.

1. Test c.1: proportion and 95% CI of cases accepting randomisation.

D. Document study throughput.

1. Test d.1: proportion and 95% CI of cases randomised completing treatment (definition of completing= 80% of offered sessions).

2. Test d.2: proportion of cases attending each session (6 proportions and 95% CIs).

4. Acceptability of treatment: means and ranges of client satisfaction survey. See also qualitative methods for client experience of treatment interviews.

E. Establish the feasibility and acceptability of baseline and outcome assessments.

1. Test e.1: proportion and 95% CI of cases with complete data. See also qualitative methods for client feedback regarding measures.

F. Identify the most appropriate primary outcome. Key assessment is participant feedback from qualitative interviews. However preliminary tests from H.2 below may also be informative.

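### Because screening weights are re-fitted during recruitment, diagnostic yield and false-negative rate may each pool several screening rules, and a re-fitted score tested in the planned ROC would look too accurate

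*Protocol*

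**What the plan says.** All references are to the protocol.

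- **Adaptation.** Section 7.2, Screening Measures, combines the ASA with the DAWBA attachment items "so that we can test the optimal configuration of items for case identification". This is to be done by expert consensus together with prediction methods that learn as data arrive, "adjusting item weights based on accumulating data from full diagnostic assessments".
- **Reference diagnosis.** Section 7.2 says of the DAWBA that "due to some limitations in its validity for assessing RAD, we rely on the DAI for this diagnosis".
- **Cut-off.** Section 6.1, Pilot RCT, states: "we will choose cases above the highest 66th percentile for symptoms of RAD (initially based on normative data". The word 'initially' foresees a later change of reference distribution.
- **What the cut-off controls.** Section 6.2: "Invitations and follow-up phone calls will be made to all foster carers reporting RAD symptoms over the screening cut-off", for the interview that establishes diagnostic status.
- **Trial entry.** Section 4.4 requires "presence of DSM-5 defined RAD". Under sections 4.4 and 6.1, if fewer than 3 of the first 15 assessed children are diagnosed, children above the screening threshold become eligible without a full diagnosis.
- **Analyses.** In section 10, test a.3 is the "proportion and 95% CI of cases where diagnosis is confirmed". Test a.4 is the proportion diagnosed in a random 25 children below the threshold. Test a.5 is an "Initial non-parametric ROC curve analysis (total N = 125), based on assumption that DAI diagnosis is gold standard". Item H of that section rests the choice of screening tool on a.4, a.5 and qualitative interviews.

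**The concern.** Two features of the plan interact.

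First, the score that selects children for the DAI is itself re-weighted from DAI results. Once the weights change, a different set of children lies above the cut-off. Children screened early and late may then be invited under different rules, while a.3 and a.4 are each defined as one proportion with one interval. A later trial could not tell which rule produced the reported yield or false-negative rate.

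Second, the children who supply diagnoses for the weights are the children on whom the ROC is run. A score fitted to a sample discriminates better in that sample than in new children.

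Objective J in section 4.2 is to establish the best screening tool, and the first reason in section 13.1 for not proceeding is failure to identify enough cases. Screening yield and accuracy are therefore among the main products of this pilot.

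**Working it through.** **1. The plan's own figure.** Section 10 sets 100 diagnostic assessments in screen-positive children and 25 in screen-negative children. 100 + 25 = 125, which is the stated ROC total. At these targets, every Phase 3 child whose DAI can inform the weights is also in the ROC, and no separate validation group remains.

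**2. Size of the optimism.** The documents give neither the number of items nor the fitting method, so the inputs below marked (A) are assumptions.

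- From the plan: 500 screened, 100 positives and 25 negatives assessed, 50% diagnosed among positives.
- (A) The top third on a plain item sum is screen-positive, approximating the 66th-percentile rule.
- (A) 6 to 20 items scored 0/1/2 with loading 0.55; no, moderate or strong link between symptoms and diagnosis.
- (A) Weights by logistic regression, nearly unpenalised or ridge; 300 replicates.
- Optimism = AUC in the 125 children used for fitting, minus AUC in new children drawn with the same 100:25 mix.

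Results for the nearly unpenalised fit (same children vs new children, difference):

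| Items | No link | Moderate link | Strong link |
|---|---|---|---|
| 6 | 0.619 vs 0.500 (+0.119) | 0.698 vs 0.625 (+0.073) | 0.765 vs 0.712 (+0.053) |
| 10 | 0.662 vs 0.500 (+0.162) | 0.738 vs 0.623 (+0.115) | 0.803 vs 0.727 (+0.076) |
| 15 | 0.696 vs 0.500 (+0.196) | 0.769 vs 0.622 (+0.147) | 0.829 vs 0.721 (+0.108) |
| 20 | 0.732 vs 0.500 (+0.232) | 0.795 vs 0.612 (+0.183) | 0.858 vs 0.713 (+0.145) |

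With ridge the differences run from +0.052 to +0.227. All 24 settings are positive, about 0.05 to 0.23. With fixed unit weights, the two AUCs agree within about 0.015.

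**3. A simpler model as a check.** This used 50 cases, 75 non-cases, independent normal items and logistic weights. With no signal, the same-data AUC is 0.61, 0.66, 0.70 and 0.73 for 5, 10, 15 and 20 items, against 0.50 in new children. With a total separation of 0.742 SD, the true AUC is Φ(0.742/√2) = Φ(0.525) = 0.70. The same-data AUC is then 0.72 to 0.80, against 0.68 down to 0.63 in new children. Cross-validation removed the optimism.

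**4. A different yardstick.** Against the AUC in all screened children (six settings with ridge, 400 replicates), same-data AUC minus whole-population AUC was:

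- 6 items: 0.701 − 0.665 = +0.036 (moderate); 0.764 − 0.779 = −0.015 (strong)
- 10 items: 0.732 − 0.675 = +0.057; 0.802 − 0.799 = +0.003
- 20 items: 0.790 − 0.671 = +0.119; 0.853 − 0.808 = +0.045

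The enriched sample lowers AUC by itself and partly offsets the optimism.

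**5. Size of the drift.** Weights were re-fitted after 50 assessments and the same percentile was recomputed on the new score. About 24% to 42% of the original top third fell below the cut-off when items were informative, and about 60% when they were not.

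**The case against.** The strongest defence is that the adaptation is deliberate and disclosed. Section 7.2 says that no fully validated screen exists and defends learning from the data because this is a feasibility trial; section 10 calls the ROC initial. That stands. It is a reason to keep the adaptation, not to leave its versions untracked.

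Several stronger readings are tempting, and the documents do not support them.

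- **That the trial's entry rule drifts.** By default, entry rests on a DSM-5 diagnosis, and the screen controls only invitation to the DAI. Drift reaches eligibility only if the 3-of-15 fallback is triggered.
- **That the ROC certainly overstates accuracy.** Test a.5 does not name its score. The ASA alone, the DAWBA items or an original composite with fixed weights would not carry this optimism. An analysis plan not shown may name the score and provide a correction. Step 4 also shows that overstatement is usual but not certain when all screened children are the yardstick.
- **That re-weighting does worse than a plain sum.** In step 3 the separation is set so that unit weights are already optimal, so fitted weights can only lose. Expert consensus, which section 7.2 also uses, is not modelled.
- **That test a.2 is equally affected.** It measures carers' agreement to assessment, and there is little reason for that to depend on item weights.
- **That the arm comparison is biased.** Screening precedes randomisation, so it is not.

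It can also be said that a percentile is easily recomputed for a new score. It is, but step 5 shows that the same percentile then selects a materially different group. Finally, neither the AUC nor a.3 is named in the numerical progression thresholds of section 13.1, and the identification-rate threshold there is coarse (below 10%). That limits the stakes for the go/no-go decision, but not for the choice of screen.

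**Conclusion.** The point holds within these limits. The protocol itself fixes both the in-recruitment re-weighting and a ROC set with no independent children. Tests a.3 and a.4 may therefore describe a mixture of screening rules, and any re-fitted score judged on the 125 would be optimistic by about 0.05 to 0.23 in AUC against new children sampled the same way. These figures are illustrative: they depend on an assumed item count, link strength and fitting method. The direction was the same in all 24 settings. The conclusion on the ROC is conditional on a re-fitted score being evaluated there, which the stated purpose of the re-weighting and item H together suggest but do not state. What is at stake is the usefulness of the screening parameters for a full trial, not the validity of the randomised comparison.

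**What to change.** 1. Keep raw item responses for every screened child, and record the score version and numerical cut-off applied to that child. Section 13 plans recruitment from February 2018 to February 2019 and this protocol version is dated January 2019, so versions for children already screened may need to be reconstructed from screening dates.
2. Report a.3 and a.4 by version, beside any pooled figure.
3. Run the main a.5 ROC on the original fixed-weight score.
4. Report any re-weighted score as exploratory, with a cross-validated or bootstrap optimism-corrected AUC, or evaluate it only on children screened after its weights were set.

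The cost is slightly more record-keeping and analysis, and a lower reported AUC for the re-weighted score. Results by version are also less precise. For example, with no diagnoses found, the exact upper 95% limit for a.4 is 1 − 0.025^(1/25) = 14% for all 25 children, but 1 − 0.025^(1/12) = 26% for a version that covers only 12.

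Locking one score and cut-off for all Phase 3 invitations is an option for the sponsor to weigh, not a required change. It would give one rule throughout but gives up the adaptation that section 7.2 chose. A cut-off taken from the roughly 100 Phase 2a screens would also be imprecise: SE = √(0.66 × 0.34/100) = 0.047, so the nominal 66th percentile could lie at about the 57th to the 75th (0.66 ± 1.96 × 0.047).
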